3.2 Secondary Objectives and Endpoints

The secondary objectives of the study are as follows:

- To explore the microbiological and overall efficacy of 3% SPL7013 Gel in the treatment of BV compared to the HEC placebo gel.
- To determine the safety and tolerability of SPL7013 Gel in the study population.
- To determine the Investigator-assessed and patient perceived symptom resolution and treatment acceptability of SPL7013 Gel in the study population.
- To assess the association of BV signs and symptoms with clinical diagnosis of BV.

These will be determined by comparison of the following Secondary Endpoints:

- "Nugent Cure" (defined as a Nugent score of ≤3 when a score of 7 or more was determined at Baseline) at Visit 3 and the TOC visit.
- "Therapeutic Cure" (defined as a composite of both "Clinical Cure" and a Nugent score of 3 or less irrespective of status at Baseline) at Visit 3 and the TOC visit.
- "Therapeutic Resolution of BV" (defined as a Nugent score of ≤6 and fulfilling the criteria of "Clinical Cure") at Visit 3 and the TOC visit.
- "Clinical Cure" at Visit 3.
- Genital AEs considered to be possibly, probably or definitely related to study product.
- All other AEs.
- Change from baseline in "Symptom Questionnaire" score at Visit 3 and TOC visit.
- "Acceptability Questionnaire" (Treatment Satisfaction Questionnaire for Medication (TSQM)) domain scores at Visit 3
- Correlation of Symptom Questionnaire responses with Nugent score at Visit 3 and TOC.
- Semi-quantitative analysis of vaginal flora (sub-set only)

4. STUDY DESIGN

This study is a double-blind, multi-center, randomized, placebo-controlled, dose-ranging study in women with a diagnosis of BV by Amsel's Criteria (all 4 criteria present) and a Nugent Score ≥4. After a maximum 1 week screening period, participants will be randomized to receive either 0.5%, 1%, 3% SPL7013 Gel or HEC placebo gel at a dose of 5g each night administered vaginally for 7 consecutive days. Participants will be assessed for BV (both by Amsel's criteria and by Nugent score) at screening, baseline, after last application on Day 7 (Day 9-12) and at the final study visit, the Test of Cure (TOC) visit approximately 2-3 weeks after last dose (Day 21-30).

At each visit participants will undergo: pelvic/gynecological examination, during which vaginal swabs will be taken (including a sample for storage); adverse events (AEs) will be recorded; a Symptom Questionnaire will be completed, and adherence to the protocol will be assessed. Acceptability questionnaires (for treatment satisfaction) will be administered after completion of treatment (Visit 3). Participants will complete Diary Cards on a daily basis to capture data on study drug administration and AEs.

The study is expected to be a maximum of 5-6 weeks in duration for each participant.

5. STUDY POPULATION

To assess any potential impact on participant eligibility with regard to safety, the investigator must refer to the IB⁷ for detailed information regarding warnings, precautions, contraindications, AEs, and other significant data pertaining to SPL7013 Gels and placebo.

5.1 Target Population

The target population for recruitment is 132 women aged 18-45 years with a diagnosis of BV by Amsel's Criteria¹⁵, who are otherwise healthy.

5.1.1 Inclusion Criteria

- 1. Women aged 18-45 years.
- 2. A diagnosis of BV defined as presentation with all of the four Amsel's Criteria¹⁵ (*i.e.* all four of the following symptoms: presence of white to grey homogeneous discharge; positive whiff test (amine odor) with addition of potassium hydroxide (KOH); vaginal pH greater than 4.5; and presence of clue cells), a Nugent score¹⁶ of ≥4, and patient reported symptoms.
- 3. Willing and able to provide written informed consent.
- 4. Healthy and with a regular menstrual cycle as assessed by medical history and medical interview.
- 5. If heterosexual or bisexual and of child-bearing potential, using an effective method of contraception and intention to use this method for the duration of study participation, including one month after cessation of study product. An "effective method of

- contraception" is defined as: surgical sterilization; documented vasectomy of partner(s); intra-uterine device inserted at least 30 days prior to entry in to the study; or hormonal contraception (non-vaginally administered).
- 6. Able to understand and willing to comply with study protocol procedures and restrictions.
- 7. Reported negative Papanicolaou (Pap) smear in previous 2 years (or in line with local guidelines) for participants over 21 years old (if not available, screening will be offered in accordance with local clinical guidance).

5.1.2 Exclusion Criteria

- 1. Presence or history of allergy to topical vaginal products, or to SPL7013 Gel, HEC placebo gel or their components.
- 2. Abnormal pelvic examination at Baseline that, in the Investigator's opinion, indicates the participant is unsuitable for the study, including presence of vulvovaginitis and/or cervicitis.
- 3. Tests positive for Chlamydia, gonorrhea or trichomoniasis infection at screening.
- 4. Use of any vaginally administered products (including douches, personal lubricants and therapeutic products) other than the study products during the screening and study periods, other than the participant's usual brand of tampons.
- 5. Participation in any other drug or device study within 30 days or 5 half-lives which-ever is the longer, or has ever received VivaGel® in a previous study.
- 6. Any social or medical condition precluding enrolment in to the study.
- 7. Recent vaginal/cervical surgery (within 3 months of screening).
- 8. Pregnant, planning to become pregnant, or breast-feeding, or within 3 months of last pregnancy outcome at enrolment.
- 9. Use of oral and/or vaginal antibiotics or antifungals within 14 days of enrolment.
- 10. Tests positive for urinary tract infection (by urine dipstick) (women may be treated for their UTI and re-screened once the infection has fully resolved and exclusion criterion 9 is fulfilled).
- 11. The Investigator considers the participant to be a an increased risk of having an accompanying STI.
- 12. In the opinion of the investigator, should not participate in the study.

5.1.3 Randomization Criteria

All inclusion and exclusion criteria must be met by each participant before they can be randomized in to the study. An exception may be made if a local test for BV is performed during screening and provides a positive result, in such cases the participant may be enrolled pending result of the Nugent symptom score. If the score is later determined to be less than 4, the participant must be withdrawn.

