7.1.2 Baseline/Enrolment (Visit 2, Day 1)

Participants deemed to be eligible after the screening assessments (Nugent score may be outstanding as above if a local test for BV returns a positive result) will return for the Baseline/Enrolment visit, which should be scheduled after complete cessation of menses. This visit will include the following procedures and collection of the following information:

- Review of protocol compliance
- Review of the inclusion/exclusion criteria (see Section 5.1)
- Review of AEs and concomitant medications (see Sections 7.3.5 and 8). AEs occurring prior to administration of first dose of study product should be entered in to the Screening Signs and Symptoms section of the CRF.
- Pelvic examination including vaginal swab for Gram stain, semi-quantitative analysis (subset only) and storage sample (see Sections 7.2.3 and 7.2.6)

- Assessment of BV according to the Amsel's Criteria
- Urine samples for pregnancy testing and urine dipstick for UTI (see Section 7.2.6)
- Completion of Symptom Questionnaire (see Section 7.2.7)
- Issue diary card and provide instructions for completion
- Re-iterate study procedures and restrictions
- Confirmation of technique for study product use
- Randomization (see Section 6.4)
- Assign PIN
- Dispense study product

Each participant is then provided with the date of the next scheduled visit, and reminded to administer study product later that day just before bed and continue dosing for the remaining 6 days as directed.

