7.1.6 Withdrawal Visit

Any participant who prematurely withdraws from the study, for whatever reason, will be asked to attend a Withdrawal Visit as soon as possible and ideally within 2 weeks of finishing study treatment administration. This includes women who enroll in to the study with a positive local test for BV but without a confirmed Nugent score of 4 or more, where the Nugent score is subsequently determined to be less than 4, and are required to withdraw. Women who require rescue therapy are not considered withdrawals unless they do not complete the TOC visit; they are classified as "Treatment Non-Responders". Follow-up procedures for female participants who become pregnant during the study are outlined in Section 7.1.7. The Withdrawal Visit will include the following procedures:

- Review of protocol compliance
- Review diary card
- Review of AEs and concomitant medications (see Sections (see Sections 7.3.5 and 8).
 Participant will be referred to her primary care physician for any ongoing AEs as appropriate. Any ongoing SAEs should be followed until resolution or considered as stable
- Pelvic examination including vaginal swab for Gram stain, semi-quantitative analysis (subset only) and storage sample (see Sections 7.2.3 and 7.2.6))
- Assessment of BV according to the Amsel's Criteria

- Pregnancy testing (see Section 7.2.6)
- Completion of Symptom Questionnaire (see Section 7.2.7)
- Completion of Acceptability Questionnaire [TSQM] (see Section 7.2.8)

Women in whom the BV has been found to recur at this Withdrawal Visit will receive rescue medication for their BV according to local practice as outlined in Section 6.8. Any rescue therapy will be documented in the participant's CRF.

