10.2.6.2 Randomized Dataset

The randomized dataset will include all participants that meet the eligibility criteria and are randomized to double-blind investigational product. In determining eligibility, and in case of discrepancies, the Nugent score obtained at screening will take precedence over the score determined centrally.

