10.2.6.3 Modified Intent to Treat Safety Dataset

The Modified Intent-to-treat (MITT) dataset will include all participants who are randomized to double-blind investigational product, administer at least one dose of study gel, and have at least one post baseline assessment of efficacy and did not receive antibiotics except as rescue medication (via any route) or vaginal antifungals. This dataset will be employed to determine all primary and secondary efficacy endpoints. Participants will be analyzed according to the treatment group in which they were randomized, irrespective of actual treatment received.

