10.8 Statistical and Analysis Plan

A final statistical analysis plan will be developed and approved by Starpharma prior to database lock. Statistical analyses will be performed after all participants have ended their participation in the study. Participants withdrawn prior to randomization will not be assessed for outcome variables or safety parameters. The following is a summary of the planned analyses; full details are captured in the statistical analysis plan. Any deviations to be made from this summary plan and planned analyses will be documented in the statistical analysis plan.

All hypotheses will be tested for statistical significance with two-tailed p-values unless otherwise noted. Results of all tests will be considered statistically significant if their p-value is less than or equal to 0.048 as per the O'Brien-Fleming α adjustment for the planned interim analysis.

Continuous variables will be summarized using descriptive statistics (N, mean, standard deviation, median, minimum and maximum), while categorical variables will be summarized as counts and percentages of participants in each category. Results will be presented by treatment group as appropriate.

Efficacy analyses will be presented using the MITT and per-protocol populations. For efficacy analyses, all missing values due to participant withdrawal and missed visits as well as values outside of analysis windows will be imputed using the last observation carried forward (LOCF) method as appropriate. For sensitivity analysis, efficacy results will also be presented with "as observed" results.

All baseline and demographic summaries will be based on the MITT dataset. No statistical comparisons between treatment groups will be made on demographic and baseline characteristics.

If there is a discrepancy between the locally and centrally read Nugent score, the locally read score will take precedence over the centrally read score in determining whether a participant is eligible to enter the study. The centrally read score will take precedence over the local score in determining study endpoints.

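### The MITT (LOCF) analysis keeps women withdrawn for a screening Nugent score below 4 and lets an early visit stand in for their TOC outcome

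*Protocol*

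**What the plan says.** **Entry.** Section 5.1.3 allows an exception when a local BV test is positive: "in such cases the participant may be enrolled pending result of the Nugent symptom score". Section 7.1.2, the visit at which women are randomised and given gel, repeats it: "Nugent score may be outstanding as above if a local test for BV returns a positive result".

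**Exit.** Section 5.1.3 continues: "If the score is later determined to be less than 4, the participant must be withdrawn". Sections 7.1.1 and 7.2.6.3 say the same of the screening score.

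**Assessment on exit.** Section 7.1.6 names this group among those asked to attend a Withdrawal Visit: "This includes women who enroll in to the study with a positive local test for BV but without a confirmed Nugent score". The visit includes an Amsel assessment and a Gram stain. It is to take place as soon as possible, ideally within 2 weeks of the end of dosing.

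**Analysis sets.** Section 10.2.6.3 defines the MITT as "all participants who are randomized to double-blind investigational product, administer at least one dose of study gel", with at least one post-baseline efficacy assessment and no antibiotics (other than rescue) or vaginal antifungals. This set serves all primary and secondary efficacy endpoints. The Randomized dataset in Section 10.2.6.2 is narrower on this point: "all participants that meet the eligibility criteria and are randomized". The Per-Protocol set in Section 10.2.6.5 also requires eligibility.

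**Missing data.** Section 10.8 says that "all missing values due to participant withdrawal and missed visits as well as values outside of analysis windows will be imputed" by LOCF as appropriate. The as-observed results are a sensitivity analysis.

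**The concern.** Each rule is understandable alone, but together they work badly. The protocol orders these women out before TOC, keeps them in the main efficacy set, and fills the gap it created with a reading taken during or soon after dosing. Keeping randomised women in the analysis normally goes with observing them to the endpoint. Here an early visit is substituted for it.

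These women fail the Nugent part of inclusion criterion 2. Therapeutic Cure (Section 10.2.4.3) and Therapeutic Resolution (Section 10.2.4.4) accept a low Nugent score whatever the Baseline status, so they may satisfy that component with no treatment effect.

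At stake is the sensitivity of a small trial planned at 28 evaluable women per arm. Section 10.3 requires the analysis to include everyone who meets a dataset definition, so an SAP that follows the protocol would have to keep them.

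**Working it through.** **1. Does the chain close?** A woman with her score pending is randomised and dosed (5.1.3, 7.1.2). Her score is below 4, so she is withdrawn and seen at a Withdrawal Visit (7.1.6). She now has one dose and one post-baseline efficacy assessment and, absent excluded drugs, is in the MITT (10.2.6.3). If dosing ends on Day 7, two weeks later is Day 7 + 14 = Day 21. A visit held as soon as possible, or after fewer doses, therefore normally falls before the TOC window of Day 21-30. Her TOC value is missing through withdrawal and LOCF applies (10.8).

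**2. The protocol's own figure.** Inputs from Sections 10.4 and 10.8: cure rates 0.50 and 0.15, two-sided alpha 0.048, power 80%, drop-out 15%. With pooled variance and no continuity correction:

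n = [z(0.976)·√(2p̄(1−p̄)) + z(0.80)·√(p1(1−p1)+p2(1−p2))]² / (p1−p2)², with p̄ = 0.325

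n = [1.977·√0.43875 + 0.842·√0.3775]² / 0.35² = 27.2, rounded up to 28. Then 28/0.85 = 32.9, rounded up to 33 per arm, and 4 × 33 = 132. The plan's figures reproduce. Power at 28 per arm is 81.1% by this approximation and 81.4% by exact enumeration of the chi-square test.

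**3. Effect of keeping these women.** Let f be their share of each arm and q their cure rate, the same in both arms. Each arm's rate becomes p(1−f) + qf, so the difference is 0.35(1−f) whatever q is. Both f and q are assumptions, because the documents give neither. With q = 50% and 28 analysed per arm:

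| Share f | Active | Placebo | Difference (points) | Exact power |
|---|---|---|---|---|
| 0 | 50% | 15% | 35 | 81.4% |
| 1% | 50% | 15.35% | 34.65 | 80.4% |
| 2% | 50% | 15.7% | 34.3 | 79.3% |
| 5% | 50% | 16.75% | 33.25 | 76.0% |
| 10% | 50% | 18.5% | 31.5 | 70.2% |

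Varying q: at f = 10%, exact power is 72.1% for q = 30% and 68.6% for q = 70%. At q = 0 it is 78.5% for f = 5% and 75.3% for f = 10%.

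**4. Effect of leaving them out.** The 35-point difference is kept and the sample falls: 28 × 0.95 = 26.6, about 27 per arm, and 28 × 0.90 = 25.2, about 25 per arm.

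| Share f | n per arm | Exact power | Normal approximation |
|---|---|---|---|
| 5% | 27 | 81.3% | 79.6% |
| 10% | 25 | 79.0% | 76.3% |

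The exact figure hardly moves from 28 to 27 because the test is discrete, so the approximation is the fairer guide to the gain. On that scale the kept-in power at q = 50% is 76.0% and 70.4%, so exclusion gains about 4 and 6 points. The exact scale suggests 5 and 9.

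**The case against.** Several points against the concern stand.

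- **The group may be tiny.** A woman must show all four Amsel criteria, report symptoms, test positive locally, then score 3 or less, and still be dosed and assessed. Section 7.2.6.3 allows local Nugent scoring, which can shorten the wait. At a 1-2% share the loss is only 1-2 points of power.
- **Other planned analyses largely avoid it.** MITT (as observed) gives these women no TOC value unless they are seen in the window, and Per-Protocol excludes eligibility violations. Section 10.9 lists both for the primary variable. But Section 10.8 makes the first a sensitivity analysis and Section 10.2.6.5 makes the second supportive.
- **LOCF applies only as appropriate, and Section 10.3 provides a blinded evaluability review.** Neither names an exception for this group, and Section 10.3 also requires inclusion of all who meet a definition.

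A reader might infer more than the documents support:

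- **That these women do not have the disease.** They met the Amsel and symptom criteria, and the primary endpoint is Amsel-based. They miss only the Nugent entry threshold.
- **That the placebo cure rate must rise.** It rises only if their cure rate exceeds 15%, and nothing in the protocol fixes that rate.
- **That they meet the Nugent part of the composites from the start.** Those endpoints score a later slide, so they may meet it but need not.
- **That the MITT should sit inside the Randomized dataset.** That dataset requires every eligibility criterion. Exclusion criterion 4 (Section 5.1.2) covers vaginal product use during the study period, so nesting would bring a post-randomisation exclusion into the main efficacy set.

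**Conclusion.** The point holds for MITT (LOCF). The text admits women withdrawn for a screening Nugent score below 4 and replaces their TOC outcome with an early one. This is a stated rule with a poor result, not a detail left to the SAP.

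The effect is dilution. It should not be read as bias between arms or as a false-positive risk: the screening slide precedes treatment, study staff are blinded (Section 10.6), and the central laboratory does not hold the randomization list (Section 6.4).

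Under a common cure rate the 35-point difference shrinks by the group's share. The loss of power is negligible at 1-2% and about 5 to 11 points at 5-10% with an assumed 50% cure rate. The share and the cure rate are assumptions. The direction is not, provided the cure rate is the same in both arms. The change is worth making because it is cheap and excluding on a blinded pre-randomisation score introduces no bias.

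**What to change.** In Section 10.2.6.3, add one condition to the MITT: the screening Nugent score that decides eligibility under Sections 7.2.6.3 and 10.2.6.2 is 4 or more. Apply it blinded and alike in every arm. Add only this condition, and do not define the MITT as a subset of the Randomized dataset. Keep these women in the Safety dataset, and add a sensitivity analysis of the efficacy endpoints that includes them. The withdrawal rule itself need not be touched for this purpose.

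The cost is one sentence, one extra table and slightly fewer women in the efficacy set.

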5.1.4 Number of Participants

A total of 132 eligible women will be recruited in to the study, such that 112 are expected to be evaluable.

Drop-outs or withdrawals (as defined in Section 9) may be replaced at the discretion of the sponsor.

5.1.5 Method of Assignment

This study is a double-blind, randomized, placebo-controlled, dose-ranging study. Participants will be allocated a unique identification number (Participant Identification Number, PIN) at randomization from a list of numbers that will be assigned sequentially. The PIN will identify the treatment group to which she has been randomized, and the package of clinical trials supplies allocated to her. The randomization list will be held by an independent third party and will not be accessible to any of the study team until the blind has been broken.

6. STUDY PRODUCTS

6.1 Investigational Product

The investigational product is 5g SPL7013 Gel, containing 0.5%, 1% or 3%w/w SPL7013, packaged in single dose applicators. The HEC placebo gel will be packaged in identical applicators. The investigational formulation and all details on the study product are described in the IB.⁷

6.2 Dosage and Administration

6.2.1 Dose and Dose Justification

The three gel strengths 0.5%, 1% and 3% w/w SPL7013 have been selected for investigation in this study based on microbiology data. The lower strength gel, 0.5%, has been selected as data indicates efficacy against *G. vaginalis* without affecting *L. crispatus*, the only *Lactobacillus* species against which SPL7013 has been shown to have activity. The higher gel strength, 3% has been selected as it provides the broadest activity (against *B. ovatus*, *P. bivia* and *G. vaginalis*), and the 1% strength selected to investigate a mid-point between the two.

The duration of treatment in SPL7013-013 is once daily vaginal administration for 7 days and is based on previous experience showing that where Nugent scores normalize in clinical studies of SPL7013 Gel completed to date, this effect appears to occur after seven days' treatment. In addition, standard antibiotic therapy for BV is usually for 5-10 days

6.2.2 Administration

Study participants are to administer study gel product once daily, at bedtime.

Participants will be instructed to administer a single dose of study product by inserting the applicator in to the vagina and fully depressing the plunger slowly and evenly to ensure application of all gel. Used applicators are to be stored in a sealed plastic bag, and returned to the site at the next visit for compliance checking, after which they will be destroyed by the site.

Participants are asked to mark the time of application in their diary cards, and/or indicate any missed doses with reasons (if applicable). Instructions (including diagrams) in the correct application of the product will be provided to subjects during the Baseline visit and also included on the diary cards.

Unused applicators are to be returned to the study site.

